6.2 Design

This is a single centre pilot, single blind, randomised, placebo – controlled study.

This has been chosen as it will demonstrate feasibility and tolerability, whilst providing early data to indicate whether tVNS may provide benefit in this setting, supporting the development of a larger RCT to establish whether it is a statistically significant benefit.

Patients may be able to tell the different between an activated device and sham (where the device is applied to the earlobe instead of the tragus). However, they will not experience both settings, and we will make no clear distinction of exactly what they should feel.

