6.7 Outcome Measures

Primary Outcome Measures – success criteria:

- Monitor tolerability for tVNS
 - Symptom severity scores of mild or moderate in less than 1/3 of participants able to report symptoms (based on Likert Scale 1-5; 1 representing no issues; 5 representing severe symptoms)
- Assess study feasibility
 - recruit >1 patient per month of recruitment
 - >80% of recruited patients completing primary outcome measures at 4 weeks follow up

These outcome measures will be collected during the participants inpatient stay over the intervention period using a data collection proforma (appendix) and taken from recruitment records kept contemporaneously. Safety assessment of SAEs / AEs will be collected each intervention day by our research team.

Secondary Outcome Measures:

- Monitor safety criteria for tVNS
 - No SAEs reported to tVNS
 - Unexpected AEs in less than 1/3 of participants
- Explore clinical outcomes including:
 - rates of clinical or radiological DCI (%)
 - inpatient mortality (%)
 - inpatient length of stay (days)
 - rate of complications: seizures, hyponatraemia, rebleed, hydrocephalus (%)
- Outcome measures using questionnaires on discharge and at 1-month
 - Disability assessment: modified Rankin Score, Barthel Index
 - Assess frequency and severity of headache: Likert scale
- Explore mechanisms of action:
 - Inflammatory markers at baseline and 5 days
- o Explore response to tVNS:
 - Near-infrared cerebral spectroscopy
 - Heart rate variability
 - Pupillary reactivity

These will be measured during the inpatient hospital stay up until discharge (Figure 1).

- Outcome measures using questionnaires at on discharge and at 4 week follow-up
 - Disability assessment: modified Rankin Score, Barthel Index
 - Assess frequency and severity of headache: Likert scale (1-10 where 1 is non-existent and 10 is extremely severe)
- Explore mechanisms of action measured at baseline and at the end of intervention (5 days):
 - Inflammatory marker analysis at baseline and 5 days (IL-1B, IL-6, IL-10, TNFa)
 - Concurrent WCC, CRP and infection will be recorded at these time points as these may confound results
- o Explore response to tVNS:
 - Near-infrared cerebral spectroscopy

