6.9 Intervention

We are using tVNS settings that are widely used in other neurological conditions (epilepsy, migraine)¹⁴. These include:

- o Pulse width 25ms
- Frequency device default (20 or 25Hz)
- Intensity below pain threshold.
- Frequency 45 minutes twice daily. On the basis of similarity to other studies, practicalities on the ward and clinical scenario

We have chosen a duration of 5 days based on the usual clinical pathway of inpatient management at the Royal Hallamshire Hospital, and have chosen to deliver the treatment twice daily to optimise the dose. This is a pilot study with feasibility outcomes and as such we will be exploring the feasibility of this treatment regimen.

The Parasym Device will be applied to the left tragus (figure 1) as this is the most common site for tVNS delivery in neurological studies and is associated with few afferents to the heart.

The intervention is aimed at supplementing routine clinical care, and as such, the doses of tVNS can be interrupted for care activities (therapy sessions, examinations, assessments etc) and resume afterwards. The overall minute duration will aim to remain 45 minutes twice daily.

[figure not shown]

Figure 1. Anatomy of the ear and the tragus (a). Parasym attached to the tragus (b)

The active intervention will be compared to sham tVNS where the vagal nerve stimulator will be attached to the earlobe instead of the tragus, in keeping with evidence that this does not cause vagus nerve stimulation and is in line with sham methods used in other studies. We do not anticipate that patients will have the intervention long enough to become familiar with the common sensations associated with true tVNS intervention. At the end of the intervention period, participants will be asked if they thought they had received true of sham tVNS to understand the blinding ability of the sham.

We will use the FNIRS Lumo ecosystem (Gower labs) to assess cerebral blood flow in the frontal lobes. We will complete a protocol where 6 optodes are placed bilaterally over the frontal and prefrontal cortices. We will complete and record resting state signals of oxyhaemoglobin and deoxyhaemoglobin for 5 minutes while patients are layed in bed with their eyes closed (or wearing an eye patch). Following the 5-minute rest phase, vagal nerve stimulation or sham stimulation will start

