6.10 Study Protocol

Patients (or their representatives if they lack capacity) who are eligible for entry into the will be approached by the treating clinical teams with information about the study. Those who are interested will be given an information sheet and time to consider the study. Those keen to participate will sign a consent form (or assent form for those that lack capacity) and baseline outcome measures will be performed.

Enrolled participants will be issued with a study number and randomised 2:1 (SealedEnvelope Ltd) stratified according to age (<65 and ≥ 65 years). They will then receive either active tVNS stimulation (tragus) or sham (earlobe), twice daily for 45 minutes per session for 5 days. We do not anticipate discharges from hospital earlier than 5 days as this is not routine practice in the neurosurgical unit.

Primary outcome measures of tolerability and feasibility will be collected daily by researchers delivering the intervention, and secondary outcome measures will be collected at the end of intervention or on hospital discharge as detailed in figure 2.

Following discharge from hospital participants will return for follow up clinic assessment at 4 weeks where questionnaire measures of functional recovery and adverse event reporting will be undertaken. After this the participants involvement in the study will be complete.

Figure 2: Study Schedule for Outcome Measures

	Baseline visit	Visit 1	Visit 2	Visit 3	Visit 4	Visit 5 (EOT)	discharge	At 4 weeks
Eligibility screening	Х							
Informed consent	Х							
Randomisation	Х							
Socio- demographic data	X							
Clinical data collection	X						X	
Questionnaires: Disability - mRS, BI, headache likert scale	X						X	X
Reporting of side effects, adverse events and tolerability		X	X	X	X		X	X
Intervention reporting – settings delivered, duration of intervention		X	X	X	X			
Pupillometry + recording of prescribed eye drops	X					X		
Heart rate variability	X					X		
fNIRS	Х					X		
Monitor blood test results (secondary outcome measures), collection of data on WCC/CRP and infection status	Х	X	X	X	X		X	
Inflammatory marker analysis	X					Х		

EOT = End of treatment; BI = Barthel Index;

fNIRS = Functional near infra-red spectroscopy

7. Data Management

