7.2 Statistical Opinion

This is a pilot study which hopes to form the basis of further grant funding for a larger study. This is a provisional study to demonstrate tolerability and feasibility. Further statistical advice would be sought should further funding be granted for future study. Primary outcome data will be reported descriptively (proportions, %).

Continuous data will be compared using parametric or non-parametric analyses depending on whether data distribution is normal or not. Categorical data will be compared using Chi-square or one-way ANOVA. However, due to the small sample size, appropriate power to detect significant differences for these measures will not be reached. This is primarily an exploratory study and most data will be reported descriptively.

Between group differences in baseline characteristics will be compared using parametric (T-Tests) and non-parametric (Mann – Whitney U, Chi squared) tests, depending on normality of distribution.

A secondary outcome of this study is safety of TVNS in patients who have suffered a subarachnoid haemorrhage. Utilising the definition of SAE, if no SAE's are reported which are deemed related to tVNS by the research team, then we can be 95% confident that the true SAE rate lies between 0 and 12%.¹⁵

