10.5 Other Ethical Considerations

PIS, PIL and consent forms attached, which state participation is entirely voluntary, will always be provided to the patient, or NOK if the patient is unconscious and then given to the patient when they have capacity. The participant or legal representative will be given adequate time to ask questions and read the additional documentation. They have the right to withdraw at any time without giving a reason and this will not affect their future medical care.

There is no anticipated direct benefit of this study to participants, but it is hoped that the information obtained will help to identify a biomarker for therapeutic application in future trials.

11. Service Users and Patient and Public Involvement

The research team have met with the PPI stroke panel on 17th November 2023 and received positive feedback with discussion points actioned.

12. Dissemination

The overall findings of this study will be presented locally to the academic directorates of Neuroscience. The research team will also aim to present the findings at international scientific meetings and will write up the findings for publication in peer – reviewed journals. The study will be registered with Sheffield Teaching Hospitals and will be advertised on the University of Sheffield website under the Biomedical Research Centre page and be registered on ClinicalTrials.org.

13. Taking the Work Forward

The pilot data generated from this project will contribute towards future grant submissions. This pilot work would look to generate an application to fund a multicentre trial involving a larger number of participants to evaluate the effect of tVNS on reducing complications following SAH. We would look to apply to an NIHR funding stream for the funding of a further study to establish whether tVNS has a statistically significant impact on improving outcomes after SAH.

14. Intellectual Property (IP)

No IP is anticipated from the completion of this study.

15. Costing Schedule

The funding for this project will be provided by the stroke research account within the Academic Directorate of Neurosciences at Sheffield Teaching Hospitals.

[name] is an academic trainee funded by the NIHR with dedicated academic time. He will be involved at all stages of the project. Masters students may be recruited to assist in participant recruitment and data collection. No additional members of staff will need to be funded.

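### SAE relatedness is judged by a team that can see the arm, and the zero-SAE criterion and 0 to 12% statement count only those judged related; all-SAE reporting by arm and a non-delivering assessor would be a cheap improvement

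*Protocol*

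**What the plan says.** **Blinding.** Section 6.2 states: "This is a single centre pilot, single blind, randomised, placebo – controlled study". Its discussion of blinding concerns only the patient. In the sham arm "the vagal nerve stimulator will be attached to the earlobe instead of the tragus" (section 6.9), so whoever fits the device sees the allocation. The heading of section 6.8 mentions breaking the blind, but its text does not say who is blinded.

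**Who collects what.** Section 6.10: "Primary outcome measures of tolerability and feasibility will be collected daily by researchers delivering the intervention". Section 6.7: "Safety assessment of SAEs / AEs will be collected each intervention day by our research team". For the secondary outcomes, section 6.10 gives timing but no assessor. Section 7.1 places researchers on the ward to record data and has every researcher trained in the outcome measures. Section 8.2 makes the principal investigator responsible for both collection and analysis of outcome data.

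**What counts for safety.** The criterion in section 6.7 is "No SAEs reported to tVNS". Section 7.2 gives its 95% range of 0 to 12% for the case "if no SAE's are reported which are deemed related to tVNS by the research team", and presents it as a range for the true rate of SAEs.

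**What is reported anyway.** DCI, inpatient mortality, seizures, hyponatraemia, rebleed and hydrocephalus are secondary outcomes given as percentages (section 6.7). Section 7.1 compares the two groups and reports complication rates descriptively.

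**The concern.** Serious events caused by the disease itself are to be expected after aSAH, and each one in a treated participant calls for a view on whether tVNS contributed. Here that view is taken by a team whose members deliver the sessions and know the arm. Section 10.1 also records that the team regards the intervention as already well supported on safety. The criterion allows no related event, so the safety conclusion rests on those judgements. The 0 to 12% statement then carries the related-only count over to the SAE rate in general.

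A comparison of all SAEs by arm would not depend on attribution, but the protocol does not call for one. Assessor-rated outcomes such as mRS and Barthel are exposed in a similar way if the scorer delivered the sessions, and the protocol does not rule that out. At stake is the safety statement, and the early signals of effect, that a larger trial would draw on.

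**Working it through.** **1. Reproducing the plan's figure.** With 0 events in n participants, the exact two-sided 95% upper limit is 1 − 0.025^(1/n).

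- n = 30: 1 − 0.025^(1/30) = 0.1157, or 11.6%, which rounds to the stated 12%.
- The alternatives at n = 30 do not match: one-sided exact, 1 − 0.05^(1/30) = 9.5%; rule of three, 3/30 = 10%.

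The stated figure is therefore correct arithmetic for 0/30. Two features matter here. Its numerator is SAEs judged related, not all SAEs. Its denominator is all 30 participants, including sham participants, in whom a judge who knows the arm has little reason to attribute an event to tVNS. Counting treated participants only, 0/20 gives 16.8% (2:1 as in section 6.10, assuming active is the larger arm) and 0/15 gives 21.8% (15 per arm as in the synopsis).

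**2. How many causality calls might arise.** Sections 3 and 5 put DCI at up to 30%, which is a ceiling.

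- Both arms: 0.30 × 30 = 9 at most.
- Active arm of 15: 0.30 × 15 = 4.5 at most.
- Active arm of 20: 0.30 × 20 = 6 at most.

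Deaths, seizures, rebleeds and hydrocephalus could add to these or overlap with them; the protocol gives no rates for them.

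**3. Sensitivity of the criterion to the judgement.** Suppose the team classes a share s of truly related SAEs as related. The documents give no value for s, so the range is illustrative. Take n = 30, as section 7.2 does. With none classed as related, the upper limit on the true related rate is 11.57%/s. With an assumed true related rate of 10%, the chance of meeting the criterion is (1 − 0.10 × s)^30.

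| s | Upper limit, 0/30 | Chance of passing at a true 10% |
|---|---|---|
| 1 | 11.6% | 0.90^30 = 4.2% |
| 0.75 | 15.4% | 0.925^30 = 9.6% |
| 0.5 | 23.1% | 0.95^30 = 21.5% |

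A blinded judge would not change the 11.6% itself. What changes is how far a count of zero can be trusted.

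**4. Who might score the compared outcomes.** Section 6.10 ties the deliverers to the primary outcomes only. Sections 7.1 and 8.2 make it plausible that the same people score mRS and Barthel, but do not say so. The documents therefore support only that the overlap is not prevented.

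**The case against.** The strongest reply has five parts.

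- **The sentence about deliverers covers only the primary outcomes.** Recruitment and completion are counts, tolerability is scored in participants able to report symptoms, and section 7.2 reports these as proportions without a comparison of arms. This stands. A reader might infer that deliverers are stated to score mRS, Barthel and headache, or that the arm comparisons are shown to be biased. The documents name no assessor and support neither. Headache is also a symptom score, for which the participant's own blinding matters most, and section 6.9 checks that with an end-of-treatment guess.
- **Named complications are already reported whatever their cause.** This stands for DCI, death, seizures, hyponatraemia, rebleed and hydrocephalus. It does not cover other SAEs, and it leaves the criterion and the 0 to 12% statement resting on attribution. Table layout can be left to an SAP, but sections 6.7 and 7.2 themselves fix the related-only count.
- **Nine DCI events is not an expected number.** This stands. It is a ceiling over both arms. A single call decides the criterion only when exactly one SAE would otherwise be classed as related, and that is true of any zero-event rule. The narrower point is that the call is made with the arm known.
- **Spare staff are not assured.** Section 15 says only "Masters students may be recruited to assist in participant recruitment and data collection", which is conditional and does not extend to causality judgements. The team is small and must deliver ten 45-minute sessions per patient. This stands as a reason to make the separation subject to the rota.
- **Safety is secondary and the comparisons are declared exploratory and underpowered.** This stands, and it limits the consequence. It does not remove a directional bias if one is present.

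**Conclusion.** The point holds as a cheap improvement to the protocol. The arm is visible to the researchers delivering sessions. The zero-SAE criterion and the 0 to 12% statement count only SAEs that this research team deems related, and no blinded relatedness judgement is planned. The protocol also leaves open who scores mRS, Barthel and headache.

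At most about 9 of 30 participants would have DCI, and about 4.5 to 6 of those would be in an active arm of 15 to 20, so one unblinded call can settle the criterion. The direction and size of any bias are unknown. The widening of the upper limit from 11.6% to 23.1% rests on the assumption that only half of related events are recognised.

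A reader might also infer that existing staff could remove the bias. They could only reduce it: section 6.2 accepts that patients may tell active from sham, they may disclose what they felt, and the electrode site is visible during sessions.

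**What to change.** 1. **Sections 6.7 and 7.2, wording only.** Report all SAEs by arm regardless of relatedness, next to the related count. Describe the 0 to 12% bound as applying to SAEs judged related to tVNS, not to the true SAE rate.
2. **Sections 6.7 and 6.10, where the rota allows.** Have SAE relatedness, and the discharge and 4-week mRS and Barthel scoring, done by an existing trained team member who did not deliver that patient's sessions and is not told the arm. Section 7.1 already trains every researcher in the outcome measures, and section 7.3 places follow-up at the stroke unit, away from the neurosurgical ward where treatment is given.
3. **Sections 6.9 and 7.3.** Process fNIRS, HRV and pupil files with the arm label removed. The files already carry only a study number, so this is a small addition.

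Items 1 and 3 need no staff. Item 2 needs no new post or procedure but puts a scheduling constraint on a small team. If it cannot be met for a given patient, record who made the assessment and whether they knew the arm.

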6.3 Setting

The patients will be inpatients under Neurosurgery at the Royal Hallamshire Hospital. All outcome measures will be collected at recruitment, discharge and 1 month following discharge. They will undergo the TVNS intervention as an inpatient for 5 days.

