6.8 Subject Withdrawal, Breaking the Blind and Trial Discontinuation Rules

Participants will be advised that they can withdraw from the study at any time without giving a reason and without this affecting their clinical care. Any data already collected will be analysed with permission from the patient. A member of the research team will confirm the patient is happy to continue with the longitudinal study at their clinical follow up appointments.

We will record data including number of patients admitted with aneurysmal SAH, number eligible, number recruited, dropout rates, and reasons for these. Participants will be given the opportunity to get involved in a public patient involvement group (PPI) at completion of the study.

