7.1 Statistical Analysis

The analyses will be undertaken on statistical software (PRISM) and will compare the two groups. Rates of complications and outcomes will be reported descriptively. Data integrity will be checked by two researchers and inputted contemporaneously. Each researcher will be trained in outcome measures prior to study initiation.

We anticipate approximately 50% of participants will be unable to complete questionnaires due to confusion / low GCS etc. This is exploratory and if this is the case then these outcome measures will not be taken forward in the next stages of future trials. Otherwise we anticipate very few missing data in terms of the primary outcome measures and the objectively measured secondary outcomes due to the fact that we will have a researchers based on the neurosurgical units throughout the recruitment and intervention periods collecting and recording data.

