7.3 Confidentiality

Participant information (socio-demographic, clinical, outcome measure assessment) will be recorded on paper clinical research forms that will be furnished with a study number rather than the patient identifiers. This will then be transferred to an encrypted electronic database stored on a password protected Sheffield Teaching Hospitals research laptop, access to which will be restricted to researchers entering data and performing statistical analyses. Each study participant will be assigned a unique ID number, which will be the only "identifier" linked to data collected. A separate enrolment log will be kept updated by the researcher and held within a study file separate to the study site file. This will link these numbers to the participant's personally identifiable information. In this way, the participants' data will be "pseudo-anonymised" and no identifiable information will be kept with the actual study data.

The research laptop, study site file and enrolment log will be stored in a locked office at Sheffield Teaching Hospitals, RHH. Participants will undergo baseline and follow up data collection at the stroke unit at the RHH. Rooms there are private and data collection will be conducted in a confidential manner.

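### A clinic return is the only 4-week follow-up route described, so severely disabled survivors may be lost and the 4-week outcomes may look too favourable

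*Protocol*

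**What the plan says.** Four sections of the protocol describe follow-up after discharge, and three of them point to attendance in person.

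- Section 6.10 sets the visit: "Following discharge from hospital participants will return for follow up clinic assessment at 4 weeks". The functional questionnaires and the adverse event reporting are to be carried out there.
- Section 7.3 gives the place: "Participants will undergo baseline and follow up data collection at the stroke unit at the RHH".
- Section 6.8 ties continued participation to appointments: "A member of the research team will confirm the patient is happy to continue with the longitudinal study at their clinical follow up appointments".
- Section 6.3 starts the clock at discharge: "All outcome measures will be collected at recruitment, discharge and 1 month following discharge".

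The outcomes due at that visit are mRS, Barthel Index and the headache scale. Section 6.7 lists them as "Outcome measures using questionnaires at on discharge and at 4 week follow-up". The schedule in Figure 2 also marks side effects, adverse events and tolerability at 4 weeks. One of the feasibility success criteria in 6.7 is ">80% of recruited patients completing primary outcome measures at 4 weeks follow up".

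On who is enrolled, section 6.6 admits patients without capacity, sedated and intubated patients included, on the advice of a consultee. Section 10.1 treats their inclusion as essential to generalisability.

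On missing data, section 7.1 says: "We anticipate approximately 50% of participants will be unable to complete questionnaires due to confusion / low GCS etc". For the primary outcomes and the objectively measured secondary outcomes it expects little to be missing. Its reason is that researchers will be on the neurosurgical units during recruitment and intervention.

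**The concern.** mRS and Barthel measure dependency and mobility, and these also govern whether someone can travel to a clinic. A survivor who is bed-bound, in rehabilitation or in another hospital is plausibly less able to attend than one who has recovered well. If so, the chance that the 4-week score is missing depends on the score itself, and the observed distribution shifts towards good recovery.

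Three things would be at stake:

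- **Disability at 4 weeks.** Sections 4 and 13 intend the pilot to inform a larger trial. A 4-week disability distribution taken mainly from those fit to travel would be a poor basis for planning it.
- **Adverse events after discharge.** Events in people who do not attend could go unrecorded. The secondary safety criterion in 6.7, on the share of participants with unexpected adverse events, would then look better than it should.
- **The completion criterion.** If it covers the 4-week visit, the way the visit is held affects whether it is met.

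The reassurance in 7.1 does not reach this visit, because staff presence during recruitment and intervention ends before post-discharge follow-up. Recording dropout and its reasons (6.8) would describe the loss but would not recover the missing outcomes.

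**Working it through.** **Plan's own figure.** The protocol states no attendance, attrition or mortality rate for the 4-week visit, and the sample size of 30 carries no dropout allowance. There is no figure to reproduce, so what follows is an illustration.

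**Inputs**

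- From the protocol: 30 participants (6.5) and the threshold of more than 80% (6.7).
- Assumed: the true share of severely disabled survivors, *d*; attendance among them, *a*; attendance among other survivors, *b* = 0.95.

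**Step 1: observed share and completion, among survivors only**

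Completion = *d·a* + (1 − *d*)·*b*

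Observed severe share = *d·a* / completion

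With *d* = 0.30, the second term is 0.70 × 0.95 = 0.665.

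| Attendance of severely disabled | Completion | Observed severe share | Difference from 30% |
|---|---|---|---|
| 90% | 0.270 + 0.665 = 93.5% | 0.270/0.935 = 28.9% | −1.1 points |
| 75% | 0.225 + 0.665 = 89.0% | 0.225/0.890 = 25.3% | −4.7 points |
| 50% | 0.150 + 0.665 = 81.5% | 0.150/0.815 = 18.4% | −11.6 points |
| 25% | 0.075 + 0.665 = 74.0% | 0.075/0.740 = 10.1% | −19.9 points |

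**Step 2: sensitivity to the assumed severity, with *a* = 0.50**

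- *d* = 0.20: completion 0.10 + 0.76 = 86.0%; observed 0.10/0.86 = 11.6% against 20%.
- *d* = 0.50: completion 0.25 + 0.475 = 72.5%; observed 0.25/0.725 = 34.5% against 50%.

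If the severely disabled attend about as often as the rest, the difference nearly vanishes. At *d* = 0.30 with *a* = 1.00, the observed share is 0.300/0.965 = 31.1%, about 1 point too high. The direction therefore depends on the severely disabled attending less often.

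**Step 3: the completion criterion, if it covers this visit**

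More than 80% of 30 means at least 25, because 24/30 is exactly 80%. With independent participants and a common completion probability, the binomial chance of at least 25 of 30 is:

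| True completion | P(at least 25 of 30) |
|---|---|
| 80% | 0.43 |
| 85% | 0.71 |
| 90% | 0.93 |

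Taking all 30 as survivors, the 81.5% row of step 1 lies between 0.43 and 0.71, and the 89% row lies between 0.71 and 0.93. The 50% row of step 1 also shows that the threshold can be passed (81.5%) while the observed severe share is almost 12 points too low. Meeting the criterion would not show that selection was absent.

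**The case against.** The strongest objection is that the protocol does not rule out other routes. That is correct. A reader might infer that clinic attendance is the only permitted route, but the text supports only that it is the only one described. The data collection proforma mentioned in 6.7 is not shown and might record mode or respondent. The point survives because the mode of follow-up is a protocol procedure, and staff following 6.10 and 7.3 as written would ask participants to come in.

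Four other strong readings are tempting, and the documents do not support them.

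- **That the most disabled will drop out.** No attendance or dropout rate is given, so the loss is a risk and not an established fact.
- **That the trial's results in general will look too good.** Daily tolerability, recruitment, DCI, inpatient mortality, length of stay and biomarkers are obtained in hospital. mRS, Barthel and headache are also taken at discharge. Only what is collected at 4 weeks is exposed.
- **That the loss favours tVNS.** Similar loss in both arms would improve the outcome levels in both without by itself favouring either. Nothing in the protocol fixes a direction between arms.
- **That the completion criterion would fail through the mode of visit alone.** In step 1, completion among survivors stays above 80% down to 50% attendance. Counting an assumed 5% deaths as non-completers takes the 50% row to 0.815 × 0.95 = 77.4%, but death is not an effect of how the visit is held. Visit mode alone breaches the threshold only under harsher assumptions, such as 25% attendance at *d* = 0.30. Losses would in any case lower this criterion, not flatter it.

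It is also unclear whether that criterion concerns this visit. Sections 6.7 and 6.10 have the primary measures collected in hospital, the synopsis version does not mention 4 weeks, and mRS and Barthel are secondary.

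Finally, 7.1 already expects about half of participants not to complete questionnaires and would then drop those measures from later trials. This reduces the weight of the 4-week distribution for planning. But the cause named there is confusion or low consciousness, not travel. It plausibly selects in the same direction, and no carer route is described for it either.

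**Conclusion.** The concern holds as a risk to the 4-week outcomes only. The trial enrols severely ill patients and describes a single, in-person route for the follow-up visit, so loss related to the disability being measured is plausible and nothing in the protocol guards against it.

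Under the assumed rates, with 30% severely disabled and 95% attendance among the rest, the shortfall in the observed severe share runs from about 1 point at 90% attendance to about 12 points at 50%. True severity and attendance are not documented, so these figures show direction and order of size, not a prediction. For headache, a too-favourable result further assumes that headache is worse among those lost. For adverse events, under-reporting assumes that events in non-attenders are not picked up by another route.

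The effect on the completion criterion is conditional on 6.7 meaning the 4-week visit.

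The outcomes concerned are mostly exploratory and will be reported descriptively, so this is an improvement worth making because it is cheap. It does not undermine the trial's in-hospital findings.

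**What to change.** Add to sections 6.10 and 7.3: where a participant cannot attend, the 4-week mRS, Barthel Index, adverse events and, where the participant can report it, headache score are obtained by telephone or video from the participant or a carer, or at the bedside if the participant has been transferred or readmitted. The bedside option is limited to those cases because follow-up runs from discharge. The consultee already foreseen in 6.6 may be a ready contact for participants without capacity.

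Record mode and respondent on the case report form. Report 4-week completion by mode, by arm and by discharge mRS, so that any remaining selection can be seen against a score taken before the visit.

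The cost is a short protocol amendment and an added form field, with the same staff. The downside is small: mixed modes and proxy respondents add some measurement variation, which the recorded mode and respondent allow a reader to judge.
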